3.2 Device Usage and Safety

The SinuSonic consists of a fully-disposable medical grade silicone nosepiece mounted to a resin body. The device is equipped with a flutter valve located at the top of the device which creates gentle, self-guided oscillating expiratory resistance.

4.0 Inclusion and Exclusion Criteria/ Study Population

The study population will consist of individuals present for care at the Otolaryngology clinics at the Medical University of South Carolina with nasal congestion, friends/family members of patients presenting for care at MUSC’s Otolaryngology clinics.

Inclusion Criteria

- Adults \geq 18 years of age
- Complaints of nasal congestion present for 2 weeks or more and a qualifying nasal congestion score of >5 (10 point VAS scale).

Exclusion Criteria

- Fixed structural cause of nasal congestion (moderate or severe septal deviation, moderate or severe nasal valve collapse, Grade 3-4 polyp)
- Inability to read and understand English
- Allergic sensitivity to silicone or any other component of device
- History of severe nose bleeding within last 3 months
- Anticoagulation (Aspirin ok)
- Known pregnancy
- Current nasal crusting or ulceration revealed on rhinoscopy
- Inability to perform treatment due to underlying medical condition

- Topical decongestant use in last week

5.0 Number of Subjects

This is a pilot study. The anticipated study population is 40 subjects.

6.0 Setting

Research will be conducted at the Medical University of South Carolina. Potential participants screening as well as the 2-week post treatment assessment will take place in the outpatient sinus clinics. The 4-6 week assessment will be done via emailing of surveys.

7.0 Recruitment Methods

MUSC Otolaryngologists will notify the study coordinator (SC) of potential participants through the Sinus Clinic. If the patient is interested, the SC will approach them and explain the study in further detail and begin the informed consent process.

8.0 Consent Process

Patients who are deemed eligible for this study will be approached by the Principal Investigator or Co-Investigator in the Sinus Clinic at the Medical University of South Carolina about the study. A member of the study team will describe in full detail the study and the informed consent form to the potential subject. The prospective participant will be given adequate time to review the informed consent form and ask any questions that they have before the consent is obtained. Participants will be given a signed copy of the ICF.

8.1 Withdrawal

At any point during the study, a subject may withdraw from the study.

9.0 Study Design / Methods

This study is designed as a pilot study.

Data will be collected by the ENT fellows as well as the subjects themselves throughout the entirety of the study. The data will consist of answers from subjects for questionnaires asked by the clinicians as well as self-reported answers from the subjects.

Safety will be monitored throughout the study based on monitoring of adverse events, performing nasal, measuring vital signs (i.e. blood pressure, pulse) and weight, and through collection of concomitant medication information.

The period of observation for collection of non-serious adverse events extends from the time the subject gives informed consent until completion of the End-of-study visit or Early Termination Visit. Serious adverse events (SAE) will be reported from the time of informed consent through 30 days after the last use of the SinuSonic. Adverse event data listings will be reviewed by SinuSonic at regular intervals throughout the study. In addition, SinuSonic will be alerted of Adverse Events of interest via automated emails programmed in the EDC system.

9.1 Schedule of Events

Phase	Screening	Treatment		
		0	2	4-6
Week	0	0	2	4-6
Visit	1	2	3	4
Informed Consent	x			
Inclusion/Exclusion Criteria	x			
Medical History	x			
Height	x			
Rhinoscopy	x		x	
Vital Signs	x			
Pregnancy Test	x			
Distribution of SinuSonic	x			
NOSE Questionnaire	x		x	x
SNOT-22	x		x	x
TNSS Questionnaire	x		x	x
Global Assessment of Nasal/Sinus Problems	x	x	x	x
PNIF	x	x	x	

10.0 Data Management

All analyses and graphs will be performed with SPSS 24.0, Sample Power 3.0, and Sigma Plot 10.0 (SPSS, Chicago, IL.). Disease information and demographic variables, such as age, gender, race, quality of life (QOL) scores, and VAS scores will be summarized using frequencies, means, and standard deviation as appropriate. Outcome metrics will be compared between baseline and 5 minutes (AIM 1), baseline and 2 weeks (AIM 2), and baseline and 4-6 weeks (AIM 3). Categorical variables will be compared using Chi Square or McNemar's test. Continuous variables will be compared using One-Way ANOVA with repeated measures followed by post-hoc analysis. Data regarding safety and patient satisfaction will be summarized for each time point. A p-value ≤ 0.05 will be considered statistically significant. Due to the exploratory nature of this study, no p-value correction (ie Bonferroni) will be applied. If appropriate, subgroup analysis can be performed based on underlying disease classification (allergic rhinitis, nonallergic rhinitis, CRSsNP, CRSwNP).

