Attachment 4: Follow Up Questionnaire**FOLLOW UP 5 MINUTES**

AFTER USING SINUSONIC, HOW TROUBLESOME ARE THE FOLLOWING SYMPTOMS? PLEASE PLACE A MARK ON THE LINE.		
	Not troublesome	Worst thinkable/troublesome
Nasal blockage/obstruction/congestion		
Nasal discharge/drainage out of the front or back of nose		
Pain/pressure in nose or sinuses		
Sense of smell		
OVERALL ASSESSMENT OF NASAL AND SINUS PROBLEMS		

[figure not shown]
[figure not shown]
Change in nasal symptoms and use of device

Please rate changes in your nasal symptoms and use of device.

Symptom	None	Mild	Moderate	High
Improvement in nasal obstruction/stuffiness	0	1	2	3
Improvement in nasal drainage/discharge	0	1	2	3
Improvement in nasal or sinus pressure	0	1	2	3
Improvement in ability to smell	0	1	2	3
Pain with use of device	None	Mild	Moderate	Severe
Comfort and ease of use	Poor	Low	Moderate	High
Bleeding:	Yes	No		

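### Read as one model per outcome, the repeated-measures ANOVA lets an unreturned 4-6 week survey remove 5-minute and 2-week data already observed, and no analysis set or missing-data rule is stated

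*Combined protocol and SAP*

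**What the plan says.** Section 10.0 sets out one comparison per aim: "Outcome metrics will be compared between baseline and 5 minutes (AIM 1), baseline and 2 weeks (AIM 2"), with baseline against 4-6 weeks as AIM 3. For continuous data it then says: "Continuous variables will be compared using One-Way ANOVA with repeated measures followed by post-hoc analysis". SPSS 24.0 is named, but no procedure.

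Section 1.0 makes a single use of the device the primary objective, so AIM 1 is the primary contrast. Section 5.0: "The anticipated study population is 40 subjects". Under Section 6.0 the 2-week assessment takes place in clinic, but "The 4-6 week assessment will be done via emailing of surveys". Section 8.1 allows withdrawal at any point, and Sections 9.0, 11.0 and 19.0 mention an early termination visit. No section defines an analysis set, a rule for missing values or an expected dropout rate.

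Section 9.1 and the attached forms give these measurement times:

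| Outcome | Baseline | 5 min | 2 weeks | 4-6 weeks |
|---|---|---|---|---|
| "Global Assessment of Nasal/Sinus Problems" and the VAS lines on the same forms (the 5-minute form is headed "FOLLOW UP 5 MINUTES") | yes | yes | yes | yes |
| "NOSE Questionnaire", SNOT-22, TNSS | yes | no | yes | yes |
| PNIF | yes | yes | yes | no |

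**The concern.** Post-hoc tests have a purpose only with more than two levels, so the natural reading is one ANOVA per outcome over all its time points. In its classical form that analysis needs a complete row for each subject. The value most likely to be missing is the emailed one. An unanswered email weeks after the clinic visit could therefore decide whether a subject's 5-minute result counts towards the primary aim.

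If non-return is random, the price is precision. If it depends on how well the device worked, the 5-minute and 2-week estimates are also biased, in a direction that cannot be known beforehand. Because the plan leaves the choice of model open, two analysts following it could report different n and different estimates for the same aim.

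**Working it through.** The plan has no figure to reproduce: it gives N = 40 with no SD, effect size, return rate or dropout rate.

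**Complete-row requirement.** The check used 40 generated subjects with four time points, 8 of them lacking the last value. A standard repeated-measures ANOVA routine rejected the unbalanced data and ran only on the 32 complete subjects. Error df were (32 − 1) × 3 = 93 instead of (40 − 1) × 3 = 117. The 8 observed 5-minute and 2-week values were lost.

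**Contrasts affected by survey non-return (from the table).**
- VAS and global items: AIM 1 and AIM 2.
- NOSE, SNOT-22, TNSS: AIM 2 only.
- PNIF: none, as it has no 4-6 week value.

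**Assumed inputs for the VAS.**
- Multivariate normal, means 7 / 5.5 / 5.5 / 5.0, SD 2.
- Correlations: baseline with later times 0.70 / 0.50 / 0.45; 5 min with 2 weeks 0.55; 5 min with 4-6 weeks 0.50; 2 weeks with 4-6 weeks 0.70.
- Baseline kept only above 5 and up to 10, following Section 4.0 ("a qualifying nasal congestion score of >5 (10 point VAS scale"). This treats the qualifying and baseline VAS as one measure, although their recall periods differ (Attachments 1 and 2).
- After restriction: baseline mean 7.29 and SD 1.29; mean changes 1.59 / 1.64 / 2.16; change SDs 1.48 / 1.85 / 1.92 for AIMs 1 / 2 / 3.
- Non-return of 10/20/30%, either random or logistic in the standardised 2-week change.

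**Random non-return.** SE for AIM 1 = 1.48/√n, and the relative rise is √(40/n) − 1.

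| Non-return | n | SE | Rise |
|---|---|---|---|
| 0% | 40 | 0.234 | – |
| 10% | 36 | 0.247 | 5% |
| 20% | 32 | 0.262 | 12% |
| 30% | 28 | 0.280 | 20% |

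There is no bias. The percentage rise does not depend on the SD, so it also applies to the 2-week NOSE, SNOT-22 and TNSS contrasts.

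**Non-return related to the 2-week change.** Shift = mean change in complete rows minus mean change in everyone (VAS points). The sign depends on who fails to reply.

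| Odds ratio per SD | Aim | 10% | 20% | 30% |
|---|---|---|---|---|
| 2 | AIM 1 | 0.04 | 0.07 | 0.11 |
| 2 | AIM 2 | 0.12 | 0.24 | 0.35 |
| 2.7 | AIM 1 | 0.05 | 0.10 | 0.14 |
| 2.7 | AIM 2 | 0.17 | 0.32 | 0.47 |

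At 30% non-return, the largest AIM 1 shift is 0.14/0.280 = 0.5 SE. The AIM 2 SE is 1.85/√28 = 0.35, so the AIM 2 shift is 0.35/0.35 = 1.0 SE at odds ratio 2 and 0.47/0.35 = 1.3 SE at odds ratio 2.7.

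**Using all observed data.** If only the last survey is missing, AIMs 1 and 2 keep n = 40 with no shift. With paired comparisons AIM 3 still shifts by 0.08/0.16/0.24 (odds ratio 2). An unstructured mixed model removes that shift to within about 0.01 if data are missing at random.

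**A second, simpler model.** This assumed a mean change of 0.5 SD, correlation 0.5 between the 5-minute and 2-week changes, odds ratio 2.7, and poor responders not replying. Complete rows raised the 2-week change from 0.50 to 0.59/0.67/0.75 SD and the 5-minute change to 0.55/0.58/0.63 SD at 10/20/30%. The 2-week shifts agree with the VAS model (for example 0.47/1.85 = 0.25 SD at 30%). Random loss gave no bias. It widened the 95% CI half-width from 0.320 SD to 0.338/0.361/0.388 SD and cut power for an assumed 0.45 SD change from 79% to 75/69/63%.

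**The case against.** The strongest reply is that the loss is conditional. Section 10.0 first lists three two-time-point comparisons; if each is analysed separately, nobody leaves AIMs 1 and 2. Even a single ANOVA can use incomplete rows if it is fitted to long-format data with subject as a blocking factor, and no SPSS procedure is named. This stands: what is documented is an unstated choice, not a decision to drop subjects. But the post-hoc wording favours one model, and the usual repeated-measures routine for that model deletes incomplete rows.

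The effect on the primary aim is also modest, and in the simulated scenario no conclusion would change. AIM 1 goes from 1.59/0.234 = 6.8 SE to (1.59 − 0.11)/0.280 = 5.3 SE at 30% and odds ratio 2. AIM 2 at its worst is (1.64 − 0.47)/0.35 = 3.3 SE. This stands for changes as large as those assumed; smaller changes would lose power, as the second model shows. Payment per visit (Section 15.0) may also encourage return.

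Two further limits are fair:
- The simulated changes of 1.59 / 1.64 / 2.16 include regression to the mean from selecting on baseline. The unrestricted means give 1.5 / 1.5 / 2.0. They are not device effects, but this does not alter the shifts, which compare complete rows with everyone under the same selection.
- Keeping n = 40 for AIM 2 assumes that everyone attends week 2, which Section 8.1 does not guarantee.

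Finally, an unstructured mixed model is a lot of machinery for a pilot of 40 when paired comparisons already protect AIMs 1 and 2. That is a reason to offer both forms, not to leave the text as it is.

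**Conclusion.** The concern holds, with medium confidence about its practical effect. The absence of an analysis set, a missing-data rule and a stated model structure is certain. The loss of observed data depends on the one-model reading, on a routine that needs complete rows, and on some surveys not being returned.

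Under those conditions the cost is 5 to 20% in standard error for 10 to 30% random non-return. With response-related non-return, AIM 1 on the VAS shifts by at most about half an SE, and AIM 2 by about one SE at 30% with odds ratio 2. All rates, odds ratios, means and correlations are assumptions. The AIM 1 loss is confined to the VAS and global items. The change should be made because it is cheap and keeps observed data in the primary contrast of a small study.

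**What to change.** Replace the ANOVA sentence in Section 10.0 with one of two forms.

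Mixed-model form:

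> Each continuous outcome will be analysed with a linear mixed model for repeated measures (SPSS MIXED), with visit as fixed effect and unstructured covariance, using all observed data. Contrasts against baseline, with contrast-specific SEs and 95% CIs, will be reported where the outcome is scheduled: AIMs 1-3 for VAS/global items, AIMs 1-2 for PNIF, AIMs 2-3 for NOSE, SNOT-22 and TNSS. The n per contrast and the 4-6 week return rate will be reported.

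Simpler acceptable form:

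> Each aim will be a paired comparison with baseline using all subjects observed at both times, with n per contrast and the 4-6 week return rate reported.

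With either form, the section should also say who belongs to the analysis set (for example all enrolled, or all who used the device).

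The paired form fully protects AIMs 1 and 2 when only the last survey is missing, but AIM 3 then uses returners only. The mixed model's extra gain is confined to AIM 3 and relies on data being missing at random. It estimates 4 × 5/2 = 10 covariance parameters for the VAS and 3 × 4/2 = 6 for outcomes with three time points, from 40 subjects. Either form is a short text change using software already named, with no added data or visits.

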11.0 Provisions to Monitor the Data to Ensure the Safety of Subjects

Safety will be monitored throughout the study based on the monitoring of adverse events, performing nasal exams, measuring vital signs (i.e. blood pressure, pulse) and weight, and through the collection of concomitant medication information.

The period of observation for collection of non-serious adverse events extends from the time the subject gives informed consent until the completion of the End-of-Study visit or Early Termination Visit. Serious adverse events (SAE) will be reported to the MUSC IRB and to the sponsor from the time of informed consent through 30 days after the last use of the SinuSonic. Adverse event data listings will be reviewed by Principal Investigator and the research team at regular intervals throughout the study.

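### Early withdrawal triggers no safety form, and safety is summarised only per time point, so pain and bleeding rates among form completers may understate harm

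*Combined protocol and SAP*

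**What the plan says.** **Collection window.** Section 9.0 collects non-serious adverse events from consent "until completion of the End-of-study visit or Early Termination Visit". Section 11.0 says the same ("until the completion of the End-of-Study visit or Early Termination Visit"), and so does Section 19.0. Serious events have a separate window that is not tied to a visit: "from the time of informed consent through 30 days after the last use of the SinuSonic".

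**Schedule of Events (Section 9.1).** There are four numbered visits: screening at week 0, treatment at week 0, week 2, and weeks 4-6. No column is called End-of-study or Early Termination, and there is no adverse-event row. The last contact is remote: "The 4-6 week assessment will be done via emailing of surveys" (Section 6.0).

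**Withdrawal (Section 8.1).** The whole section is one sentence: "At any point during the study, a subject may withdraw from the study". It mentions no exit contact, form or reason.

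**Solicited safety items.** Pain with the device and bleeding are asked on the 5-minute form (Attachment 4), the 2-week form (Attachment 5) and the 5-week form (Attachment 7). Willingness to use the device again and to recommend it is asked only on the last two.

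**Analysis (Section 10.0).** The only rule is "Data regarding safety and patient satisfaction will be summarized for each time point". It names no safety population, denominator, cumulative incidence or handling of missing forms.

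**The concern.** Safety is part of the primary aim and of both secondary aims, and Section 12.0 lists pain and nose bleeds as device risks, with the degree of pain unknown. A subject who withdraws from the study because of one of these is the subject a safety summary most needs to count. As written, such a subject has no scheduled occasion to answer the home-use safety items if withdrawal falls between two forms.

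A table built at each time point from the forms in hand then describes people who tolerated the device well enough to remain. Pain and bleeding could look rarer, and willingness to use again higher, than among everyone who started. In a 40-subject study a few people can change the figure that goes forward to a later trial.

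**Working it through.** The plan gives no safety rate, dropout rate or precision target, so there is no figure of its own to reproduce. The check has two parts.

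**1. Can the solicited items be missing while the plan is followed?**
- A subject may withdraw at any time (Section 8.1).
- After the 5-minute form, the next pain and bleeding items come at 2 weeks, then at the 4-6 week survey (Section 9.1; Attachments 5 and 7).
- The Early Termination Visit that could fill the gap has no column and no listed content.

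So yes: a subject who withdraws between the 5-minute form and week 2 can leave no home-use pain, bleeding or willingness answer without any departure from the protocol.

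**2. How much could this matter?**

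Input from the plan: N = 40 ("The anticipated study population is 40 subjects", Section 5.0). Assumed, because the documents give nothing: *a* subjects are affected by bleeding or pain; *w* of them withdraw before the form; nobody else withdraws; affected subjects who stay report it on the form; and the table uses form completers as denominator.

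- Cumulative rate over all treated = *a*/40.
- Rate shown at the time point = (*a* − *w*)/(40 − *w*).
- Exact (Clopper-Pearson) 95% limits for *x*/*n*: lower = Beta quantile 0.025 with parameters (*x*, *n* − *x* + 1), or 0 if *x* = 0; upper = Beta quantile 0.975 with parameters (*x* + 1, *n* − *x*).

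| Affected *a* | Cumulative (95% CI) | Shown if none withdraw | Shown if half withdraw | Shown if all withdraw (95% CI) |
|---|---|---|---|---|
| 2 | 2/40 = 5.0% (0.6-16.9) | 5.0% | 1/39 = 2.6% | 0/38 = 0% (0-9.3) |
| 4 | 4/40 = 10.0% (2.8-23.7) | 10.0% | 2/38 = 5.3% | 0/36 = 0% (0-9.7) |
| 6 | 6/40 = 15.0% (5.7-29.8) | 15.0% | 3/37 = 8.1% | 0/34 = 0% (0-10.3) |
| 8 | 8/40 = 20.0% (9.1-35.6) | 20.0% | 4/36 = 11.1% | 0/32 = 0% (0-10.9) |

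The understatement is the cumulative rate minus the rate shown. If half withdraw, it runs from 5.0 − 2.6 = 2.4 points to 20.0 − 11.1 = 8.9 points. If all withdraw, it runs from 5 to 20 points. If none withdraw, it is zero.

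The direction depends on withdrawal being related to harm. If the same fraction *d* of affected and unaffected subjects withdrew, the rate shown would be *a*(1 − *d*)/[40(1 − *d*)] = *a*/40, which is unbiased.

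**The case against.** The strongest reply is that adverse-event capture does not rest on the questionnaires. Section 19.0 requires all adverse events, whatever their seriousness or relationship to the device, to be reported from consent until that patient's end of study. It also requires them to be followed to recovery or stabilisation, if need be past the last planned visit. Section 9.0 describes adverse-event listings and automated alerts. Serious events run to 30 days after last use. A nosebleed that leads to withdrawal is therefore reportable. This stands, and it limits the point to the solicited items and to tables built from them. It does not remove the point: no scheduled contact prompts the site to ask a home user who withdraws, and Section 10.0 plans no adverse-event incidence over all treated subjects.

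A reader might go further and infer four things that the documents do not support:

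- **That subjects who stop are excluded from the safety rates.** No section says so. The denominator is undefined; completers are one possible reading.
- **That stopping the device means missing the forms.** Section 8.1 concerns withdrawal from the study. A subject who stops using the device can still attend week 2, where rhinoscopy is scheduled and pain and bleeding are asked, and payment is per visit (Section 15.0).
- **That adverse-event collection closes at week 2, before the last home-use phase.** Visit 4 is the last numbered visit and Section 2.0 describes a study of 4 to 6 weeks. Visit 4 is the natural End-of-study visit even though it is done by email.
- **That absence from the Schedule means absence from the study.** The Schedule also omits concomitant medication and the device-use items, which the text or the attachments provide for.

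It is also fair to say that this is an exploratory pilot with no safety threshold, and that the intervals in the all-withdraw case overlap (for 4 affected, 0-9.7% against 2.8-23.7%).

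**Conclusion.** The point holds as a specification gap with a cheap remedy, not as a demonstrated bias. It is established that the plan names an early termination assessment it never schedules, asks nothing of a subject who withdraws, and states only a per-time-point safety summary with no denominator. It follows that solicited pain, bleeding and willingness answers may be missing for subjects who withdraw between forms.

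Whether rates are understated, and by how much, cannot be known from the documents. Understatement requires three things together: withdrawal related to bleeding or pain, tables computed on form completers, and no use of adverse-event records over all treated subjects. Under those conditions, an assumed 4 of 40 affected would appear as 5.3% if half of them withdraw and 0% if all do, against 10%. If any of the three fails, the systematic understatement shown here does not arise. The illustration gives the direction and possible scale; it is not an estimate.

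**What to change.** 1. **Section 8.1 and the Schedule.** Add an early-withdrawal column. Ask subjects who withdraw to complete the existing device-use items of Attachments 5 and 7 (pain, comfort, bleeding, willingness) by email or phone, with one added question on the reason for stopping. An adverse-event row in the Schedule would complete this.
2. **Section 10.0.** Make the main safety summary cumulative: the number of subjects with any bleeding, any moderate or severe pain, or device-related stopping, drawn from both the forms and the adverse-event records, over all subjects who used the device at least once. Give exact 95% intervals. Keep the per-time-point tables, with the number of forms received shown beside each.
3. **Sections 9.0, 11.0 and 19.0.** State that Visit 4, the 4-6 week survey, is the End-of-study visit.

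The cost is protocol wording, one extra question and one short remote contact per early withdrawal. No clinic visit is added and no clinical rule changes. The reported safety figures may be slightly less favourable.

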1.0 Objectives / Specific Aims

- Primary: To determine the safety and efficacy of a single SinuSonic intervention.
- Secondary: Secondary objectives of this study is to determine:
 - the safety and efficacy of a twice daily SinuSonic intervention over 2 weeks.
 - the safety and efficacy of a twice daily SinuSonic intervention over 4 to 6 weeks.

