number of antibiotics have been approved for the treatment of acute sinusitis; however, there is no conclusive evidence that oral antibiotics, topical antibiotics, or topical antifungal agents are effective in the treatment of chronic sinusitis, and their use remains controversial, particularly due to concerns over emerging resistance (Ebbens 2006; Fokkens 2007; Videler 2008). As chronic sinusitis is characteristically an inflammatory disease, the anti-inflammatory effects of corticosteroids could be expected to be of benefit. There are no clinical studies published on the use of systemic corticosteroids for the treatment of chronic sinusitis without polyps, although there is evidence that systemic corticosteroids are effective at reducing the size of nasal polyps and improving rhinitis symptoms (Fokkens 2007; Van Zele 2010). Medical treatment with nasal corticosteroids (as currently available for treatment of rhinitis) is considered a first step in the treatment of chronic sinusitis; however, the data on sprays or drops does not suggest they are very effective.

Patients with chronic sinusitis currently have limited medical options for treatment and no medication is approved for the treatment of chronic sinusitis. Standard nasal spray pumps suffer from a number of drawbacks and they are considered suboptimal for reliable drug delivery to target sites beyond the nasal valve (Aggarwal 2004). Current congestion medications are not always fully effective. This study aims to test the safety and efficacy of the SinuSonic device on adults with moderate to severe nasal congestion. SinuSonic is a medical device that utilizes sound and pressure combined with normal breathing to relieve nasal congestion. The study will take place over the course of 4 to 6 weeks starting with a baseline assessment. This study will use patient responses to measure how effective SinuSonic devices are in treating adults with moderate to severe congestion in adults.

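### The primary aim names no outcome or decision rule for efficacy, and Section 10.0 tests unranked metrics at 5 minutes, each at p ≤ 0.05 without correction

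*Combined protocol and SAP*

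**What the plan says.** The primary objective in Section 1.0 reads "Primary: To determine the safety and efficacy of a single SinuSonic intervention". No scale, time point or success threshold goes with it.

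Section 10.0 supplies the comparison but not the outcome: "Outcome metrics will be compared between baseline and 5 minutes (AIM 1), baseline and 2 weeks (AIM 2), and baseline and 4-6 weeks (AIM 3"). The metrics are not listed or ranked. On testing, the section says "Continuous variables will be compared using One-Way ANOVA with repeated measures followed by post-hoc analysis", then "A p-value ≤ 0.05 will be considered statistically significant", and declines any adjustment: "Due to the exploratory nature of this study, no p-value correction (ie Bonferroni) will be applied". It does not say whether tests are one- or two-sided, or whether the post-hoc comparisons require a significant overall ANOVA.

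Section 2.0 gives a partial pointer to the intended outcome. It describes a device meant to relieve nasal congestion and says "This study will use patient responses to measure how effective SinuSonic devices are". Section 9.1 also schedules PNIF, a measurement rather than a questionnaire answer. Sections 5.0 and 9.0 describe a pilot; Section 5.0 anticipates 40 subjects.

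**The concern.** A primary objective to determine efficacy needs a rule for what would count as efficacy. Here the reader is given a set of metrics of unstated size, a threshold that applies to each one separately, and no order among them. The metric that carries the primary conclusion can therefore be chosen after the results are known.

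Two things are at stake. First, the 5% error rate belongs to each test and not to the conclusion drawn from the set. Second, a mixed result has no agreed reading. If one VAS line moved while congestion and PNIF did not, the plan gives no basis for saying whether the primary aim was met.

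**Working it through.** **No plan figure to reproduce.** The 0.05 threshold is a convention. No family-wise error rate is stated, and the 40 subjects come without power, effect size or SD.

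**Counting the metrics for Aim 1** (those with both a baseline and a 5-minute value):

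- Section 9.1, Visit 2 column: two outcome rows are marked, Global Assessment and PNIF. Strict count: 2.
- Attachment 4 (5-minute form), under "AFTER USING SINUSONIC, HOW TROUBLESOME ARE THE FOLLOWING SYMPTOMS? PLEASE PLACE A MARK ON THE LINE": five VAS lines (blockage, discharge, pain/pressure, smell, overall assessment). Attachment 2 has the same five at baseline. Adding PNIF: 5 + 1 = 6.
- Attachment 4 also has four improvement ratings. They have no baseline value and are not counted.

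The documents do not say whether the Global Assessment row means the single overall line or the whole VAS block, so the count is two to six.

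**Chance of at least one p ≤ 0.05 with no true change, independent metrics:** 1 − (1 − 0.05)^k.

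- k = 2: 1 − 0.95² = 0.0975
- k = 6: 1 − 0.95⁶ = 0.265

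**Correlated metrics.** Simulated paired t-tests, n = 40, two-sided 0.05, one common correlation between change scores, 40,000 runs:

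| Correlation | 2 metrics | 6 metrics |
|---|---|---|
| 0.5 | 9.3% | 20.7% |
| 0.7 | 8.4% | 16.7% |
| 0.9 | 6.8% | 11.3% |

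**If a significant overall ANOVA is required first.** Simulated with VAS lines at four times and PNIF at three, n = 40, 20,000 runs, no change at any time:

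- Six metrics: 10.9%, 9.4% and 7.5% at correlation 0, 0.5 and 0.7.
- Two metrics: the independent six-metric figure implies 1 − (1 − 0.109)^(1/6) = 0.019 per metric, hence 1 − (1 − 0.019)² = 0.038. Direct simulation of one VAS line and PNIF gave 4.2%. On this mildest reading the rate is below 5%.
- The gate protects only when nothing changes at any visit. With a shift of one SD (assumed) from 2 weeks on and none at 5 minutes, the later change opens the gate. Six independent metrics are then back at 26%.

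**Counting improvements only** (2.5% per test):

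- k = 2: 1 − 0.975² = 0.049
- k = 6: 1 − 0.975⁶ = 0.141; about 11% and 8% at correlation 0.5 and 0.7
- Six metrics, gated: 5.9%, 4.3% and 4.0% at correlation 0, 0.5 and 0.7

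The benchmark for one named metric is 2.5%.

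**The case against.** The strongest reply is that this is a declared exploratory pilot, that the absence of correction is disclosed, and that no sentence says one significant metric establishes efficacy. All of that stands. A reader might infer that the missing Bonferroni correction is itself the error, or that the plan intends to claim efficacy on whichever metric succeeds. The documents support neither. What they do is leave that choice open under an objective worded as determining efficacy.

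A reader might also take six tests, and hence 26%, as established. Six is inferred from the forms. Section 10.0 never says each VAS line is tested separately, and the Schedule marks only two outcome rows at Visit 2. Post-hoc tests following an ANOVA are also often read as gated, which brings six metrics down to about 8-11% and two to about 4%. That lowers the estimate, but the gate is not stated and gives no protection across metrics.

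A still larger figure comes from pooling all three aims. With nine metrics at 2 weeks and eight at 4-6 weeks, there are 6 + 9 + 8 = 23 contrasts, and 1 − 0.95²³ = 0.69. It does not describe the primary aim: 17 of the 23 contrasts belong to secondary aims, and independence across visits is implausible.

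Finally, the documents lean towards congestion. It is the stated target in Section 2.0 and the entry criterion in Section 4.0, and Section 2.0 speaks of patient responses. Scheduling PNIF does not by itself make it a rival decision outcome. But the lean is never turned into a named primary outcome.

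**Conclusion.** The concern holds in this form: Aim 1 has no primary outcome and no decision rule, and unranked metrics are each tested at p ≤ 0.05. The chance of at least one nominally significant 5-minute result with no true change is about 10% (two metrics) to 26% (six) if independent, about 8% to 17% at correlation 0.7, and about 8-11% for six metrics behind an ANOVA gate. Improvements alone give roughly half of each. Only the combination of two metrics and an unstated gate falls below 5%.

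These ranges assume 40 complete pairs, two-sided tests and a common correlation. The documents give neither correlations nor a gate, so no single figure should be quoted as the trial's error rate.

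A reader might infer that naming one metric would make 5% the error rate for a claim that the device works. It would not. This is a single-group study of people selected on a high congestion score, so regression to the mean and the lack of a control can produce a significant change without a device effect.

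**What to change.** In Section 10.0, before data are examined:

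1. Name one primary metric for Aim 1 and say that the efficacy conclusion for a single use rests on it alone. State sidedness and whether the 5-minute comparison depends on the overall ANOVA.
2. The choice is the sponsor's. The congestion VAS line best fits Section 2.0 and Section 4.0. Two caveats belong beside it: congestion VAS is also the entry criterion, and its recall period changes from the last week (Attachment 2) to after use (Attachment 4). PNIF is the alternative if its measurement before and after use is standardised; the documents give no procedure for it.
3. Name one metric each for Aims 2 and 3. For Aim 3 it must be a questionnaire or VAS measure, because PNIF is not scheduled at Visit 4.
4. Report every other metric as exploratory, with mean change and 95% CI, and not as grounds for the efficacy conclusion. No Bonferroni correction is then needed.

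The cost is wording only: no visit, procedure or sample-size change. The downside is that a significant result on another metric can no longer carry the efficacy conclusion. The change removes selection among metrics and nothing else; the single-group limitation should be stated with the results.
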